8.1.3 Yogurt Drink Manufacture

Yogurt drink manufacture is broken into two major activities, 1) preparation of the yogurt and 2) blending with other ingredients to prepare the drink. To make the yogurt, a yogurt base is formulated to contain 9.0% milk solids non-fat (MSNF), 1.3% fat and 3.0% sugar using skim milk, cream, non-fat dry milk and sugar. The wet ingredients (skim milk and cream) are mixed together and then blended with previously weighed dry ingredients (sugar and non-fat dried milk). After blending the yogurt mix is pasteurized and homogenized (2000 psi first stage, 500 psi second stage) at 83°C for 29 sec. The pasteurized, homogenized mix is pumped to fermentation tank and given an additional heat treatment of 85°C for 30 min to denature whey proteins, then cooled to 42°C prior to inoculation with 0.02% of the yogurt starter culture (YFL-

720). The inoculated mix is agitated for 15 minutes and then allowed to incubate quiescently until the pH reaches 4.6.

To prepare the yogurt drink the gel structure of the fermented yogurt is disrupted by agitation and blended with a mixture of pectin, 36 DE corn syrup solids, sugar and water. The pectin-containing mixture is prepared by heating water, sugar, 36DE corn syrup solids, and pectin to 80°C, holding for 1 hour. This mixture is then cooled to 40°C and added to the fermented white mass resulting in the unflavored yogurt drink base. To flavor the product, strawberry puree is then added to the yogurt drink. The composition of the yogurt drink is shown in Table 4 and the ingredients used in manufacture are listed in Table 5. At this point, a portion of the yogurt drink is homogenized (1500 psi first stage, 500 psi second stage) for a second time to create a drinkable consistency and packaged in plastic bottles. To prepare the yogurt drink containing BB12, an appropriate amount of (BB-12) is added to the yogurt drink, allowed to mix for 15 minutes and then homogenized and packaged as describe above. The packaged yogurt is stored at 4°C.

Table 4. Composition of Strawberry Yogurt Drink

Component	Composition in Yogurt Drink
Fat	1.0%
Milk Solids Non-Fat	6.8%
Sucrose	6.1%
Corn Syrup Solids	6.4%
Pectin	0.4%
Strawberry Puree	3.0%

Table 5. Ingredients for Strawberry Yogurt Drink

Component	Supplier	Specifications
Milk ¹	Land-O-Lakes	PMO^2
Nonfat Dry MilkSolids ³	Various approved vendors	COA ⁴
Granulated Sugar ³	Various approved vendors	COA
Corn Syrup Solids ³ (42 DE)	Various approved vendors	COA
Pectin ADM 783	DuPont, New Century, KS	COA
Strawberry Puree SN2000036366	Sensient Flavors, Amboy, IL	COA
YF-L702 (starter culture)	Chr. Hansen, Milwaukee, WI	COA
BB-12 (probiotic)	Chr. Hansen, Milwaukee, WI	COA

¹ Milk is received on an as needed basis and is purchased from Land-O-Lakes.

² Milk will be produced under and meet the requirements of the Pasteurized Milk Ordinance (PMO)

³ The supplier for nonfat dry milk, sucrose and corn syrup solids may change based on availability and price of ingredient

⁴ All ingredients will be food-grade and a will require a Certificate of Analysis (COA) from the supplier.

8.1.4 Enumeration of BB-12 from the Yogurt

The viable count of BB-12 in the product is measured the day of manufacture (Day 0) and weekly until Day 30 of shelf-life. The yogurt drink is diluted in sterile peptone water blanks (3M, St. Paul, MN) and then appropriate dilutions of the product are cultured by pour plating on an MRS-based selective bifidobacteria medium. [104] Modified MRS agar is made by adding 4.5 grams Agar (Difco, BD, Sparks, MD) to 300 ml MRS broth (Difco, BD, Sparks, MD). After autoclaving, the agar is used immediately after addition of three selective components, 1.5mL of 0.01% Dicloxacillin (Sigma-Aldrich, St. Louis, MO); 3.0 mL of 10% Lithium Choride (Sigma-Aldrich, St. Louis, MO). Plates are anaerobically incubated (VWR, West Chester, PA) at 37°C and counted after 72 hours. The final yogurt drink also is evaluated for the presence of coliforms using high sensitivity PetrifilmTM Coliform Count Plates (3MTM, Burlington, North Carolina) and PetrifilmTM aerobic plate counts according to the 17th edition of Standard Methods for the Examination of Dairy Products, #7.072 and #6.040, respectively.

8.1.5 PCR Verification of BB-12 Level in Finished Drink

To further verify the selectivity of the BB-12 agar, colonies of varying morphology are selected for identification using *B. lactis* specific PCR primers according to the method of Ventura et al. [105] Cells are lysed according to the microwave method of Bollet et al. as modified by Kullen et al. [106, 107] The sequence of the forward primer, Bflact2, is 5'-GTGGAGACACGGTTTCCC-3' and the reverse primer, Bflact5, is 5'-CACACCACACAATCCAATAC-3'. Amplicons from PCR are electrophoresed through a 2% agarose gel at 110 volts for 2 hours, stained with ethidium bromide (Promega, Madison, WI), destained with distilled water and visualized using an Alphalmager (Alpha Innotech, San Leandro, CA). The presence of amplicons of the appropriate size is taken is taken as evidence the colonies are indeed B. lactis.

8.1.6 Acceptability Testing

Pilot testing of the drink was carried out among fifteen children ages 2-7. All children were able to consume the drink without any complaints and 13 out of the 15 requested more after consuming approximately 3 ounces of the drink.

We also completed two previous studies using the same BB-12 yogurt drink in a combined total of 354 children ages 1-4 years to determine the effects of BB-12 yogurt on daycare absences. Participants consumed the same amount of yogurt we are proposing for this trial (four ounces daily) for 90 consecutive days. Only minimal adverse events were reported by 17 participants in over 30,000 total days of product consumption; all were non-serious and self-limited. High rates of compliance, over 92%, were reported in both trials, indicating the safety and tolerability of the BB-12 yogurt drink, at this dosage.[106, 107]

8.1.7 Final Product

Table 6 contains information about the initial population of BB-12 in the product as well as the results of viable count analysis conducted up through the end of shelf life for 42 separate yogurt-drink manufacturing experiments. The total solids of the product ranged from 20.53 to 22.11% with a mean of 21.2%. The fat content of the product ranged from 0.52 to 1.29% with a mean of 0.9%. The pH of the product ranged from 4.42-4.7 with a mean of 4.42 on the day of manufacture and remained relatively constant throughout shelf life. The population of BB-12 declined slowly throughout the self-life but remained within the target level (log 9 CFU/g). Viable counts of BB-12 remained about the target value in subsequent weeks (data not shown)

but we chose to set the shelf life at 30 days. Thus a 100 ml serving would supply no less than 10¹⁰ CFU per day of BB-12.

Table 6. pH and BB-12 Values for Yogurt Drink During Storage

Time	pH (± SD)	Log CFU/ml of BB 12 (± SD)
Day 0	4.41 (0.13)	8.86 (0.36)
Week 1	4.42 (0.12)	8.86 (0.32)
Week 2	4.39 (0.11)	8.65 (0.39)
Week 3	4.38 (0.12)	8.48 (0.47)
Week 4	4.42 (0.12)	8.49 (0.40)

The release criteria for the product will be similar to fresh dairy products. The proposed release criteria are shown in Table 7.

Table 7. Release Criteria for finished product.

Item	Acceptable range	Method
Total Solids	20.5-22.5%	Microwave Drying ¹
Total Fat	0.5-1.5%	NMR ¹
pН	4.1-4.7	pH Meter
Coliforms	Negative by test	Method #7.072 ²

Analysis obtained using CEM SMART Trac Fat and Moisture Analyzer, Matthews, NC

A mock nutrition facts panel for the yogurt drink is shown in **Figure 1**, as well as a sample of the label, which is placed on the final product when used as food (**Figure 2**).

²17th Edition of Standard Methods for the Examination of Dairy Products

Figure 1. Mock nutrition label for probiotic strawberry yogurt.

Figure 1. Mock	nutrition	label for pr	obiotic str
Nutrition Facts			
Serving Size: 10	0g		
Amount Per Sei	rving		
Calories 110		Calories fr	om Fat 10
		% Daily Va	alue*
Total Fat 1.5g		2%	
Saturated Fat 19	9	5%	
Trans Fat 0g			
Cholesterol 5mg	9	2%	
Sodium 55g		2%	
Total Carbohyd	rate 23g	8%	
Dietary Fiber 0g		0%	
Sugars 19g			
Protein 3g			
Vitamin A 0%	•	Vitamin	C 2%
Calcium 10%	•	Iron 0%	
*Percent Daily V			
diet. Your daily v			lower
depending on yo			
	Calories:	2,000	2,500
Total Fat	Less	65g	80g
0	than	00	0.5
Sat Fat	Less	20g	25g
Chalastanal	than	200	200
Cholesterol	Less	300mg	300mg
Codium	than	2,400mg	2,400mg
Sodium	Less than	2,400mg	2,400mg
Total	uiali	300g	375g
Carbohydrate		Judy	57 5g
Dietary Fiber		25g	30g
Calories per grar	m:	09	
Fat 9 • Carbohy		rotein 4	

Fat 9 • Carbohydrate 4 • Protein 4

Ingredients: Cultured pasteurized skim milk, sugar, corn sweeteners, strawberries, cream, nonfat milk solids, pectin, modified food starch (corn), natural flavors, sodium citrate, potassium sorbate (preservative), red 40, blue 1.

Figure 2. Mock Product Label

8.2 DOSAGE, PREPARATION AND ADMINISTRATION OF INVESTIGATIONAL PRODUCT

Enrolled participants will be given a total 7-10-day supply of the yogurt (an amount sufficient to be taken concurrently with a 7-10 course of antibiotics) with instructions to the parents/caregivers on how to administer the product. Participants will drink four (4) ounces of yogurt each day for ten consecutive days. Yogurt will be administered via mouth.

8.3 ACCOUNTABILITY PROCEDURES FOR THE INVESTIGATIONAL PRODUCT

Written records of receipt and storage of the investigational product, including date of receipt, quantity received, amount distributed to participants, and final disposition will be maintained. Any known discrepancies in the accountability will be documented. The investigator will not use the product in an investigational manner other than that provided for in the protocol; however the product is also a yogurt and the investigator requests the use of the surplus yogurt for teaching, charitable, and other educational purposes.

8.4 Product Transportation, Handling and Storage

8.4.1 While the Product is being Shipped from the Penn State Area to the Washington, DC Area

The BB-12 and control products will be transported under refrigeration in coolers packed with ice from the Penn State area via a van driven by Penn State personnel. A member of the study personnel will meet the Penn State van at a designated meeting point halfway between the two campuses. The Study personnel will then transport the products, still in its coolers with ice, the remainder of the trip to the Washington, DC area. While in transport, each cooler will be equipped with VWR® Digital Refrigerator/Freezer Thermometer with Alarm, which will alert the study personnel by audible alarm if the temperature of the coolers increased above the preset acceptable levels (between 32°F and 45°F) at any time during transport.

8.4.2 Storage After Arriving in Washington, DC Area

Once the yogurt drinks arrive at Georgetown University in Washington, DC, they will immediately be transferred to two refrigerators that are exclusively used for the study—one for Drink # 1-3 and one for Drink # 4-6. Each refrigerator is equipped with a lock and a thermometer. Study personnel will take a daily temperature reading in each refrigerator to ensure that the yogurt drinks are kept between 32°F and 45°F. Each refrigerator is equipped with a SENSAPHONE® 2.8K Weatherproof Temperature Sensor, which are connected to a SENSAPHONE® 400 Remote Monitoring and Alarm Notification System. The sensor system will trigger an alarm when the temperature falls below or rises above customizable limits (between 32°F and 45°F) or if there is a power failure, and will contact up to four study personnel phone numbers.

BB-12 and control yogurt products expire one month from the date of manufacture. The date of manufacture can be found printed on each bottle of the yogurt drink. Once a month, the study personnel will make arrangements with Georgetown University Facilities Management to dispose of the products before or on the date of expiration.

8.4.3 Transportation and Storage While being Dispensed to Participants

The products will be transported to the participants' homes in coolers packed with ice and equipped with a VWR® Digital Refrigerator/Freezer Thermometer with Alarm. Prior to each delivery, the study personnel will arrange and confirm a mutually convenient time with the parents/caregivers to ensure that they will be home to receive the drink. This ensures that the parents/caregivers can place the yogurt drinks into their home refrigerators immediately upon receipt.

8.4.4 Duration of Storage

The products are stored in the study refrigerators at Georgetown University from the day they are delivered from Penn State (same day delivery) until transported via coolers to study participants. As mentioned above, all bottles are labeled with the dates of manufacture and will thus be stored at Georgetown University until expiration—one month after the manufacture date. Extra yogurt may be delivered upon request by the parents/caregivers due to spillage, spoilage or any other reasons as needed.

8.4.5 Instructions to Participants Regarding Storage and Dosing

BB-12 and control yogurt products expire one month from the date of manufacture. The date of manufacture can be found printed on each bottle of yogurt drink. Since the drinks are only to be consumed during a 7-10-day period and deliveries to participants will coincide with the arrival of fresh product from Penn State, participants should always have enough unexpired product in their possession to continue the study. Parents/caregivers will also be advised to dispose of any product that has been left out of the refrigerator for longer than one hour. In such cases, they may contact study personnel for fresh yogurt drinks to be delivered.

8.5 ASSESSMENT OF SUBJECT COMPLIANCE WITH INVESTIGATIONAL PRODUCT

DNA extracted from stool samples collected at baseline and at day 7 will be amplified using *B. lactis* specific PCR primers, in order to assess compliance.

Collection: Stool samples from the child will be collected by the parents/caregivers into three sterile, screw-capped tubes and frozen immediately. The participants will be instructed on how to collect the samples and be provided with written, illustrated instructions. (Refer to Section 9.5, "Stool Collection Instructions for Participants.")

Transport: After collection, a member of the research team will be phoned and instructed to retrieve the samples and transport them to the laboratory. As part of their training, students and the entire research team will sign an informational sheet documenting their understanding of the risk of handling potentially infectious materials. The stool will be transported back to the lab and placed in -40° Celsius to freeze for batch transport to the Institute for Genomic Sciences at the University of Maryland Baltimore ([name] Lab). (Refer to Section 9.4, "Stool Collection Instructions for Study Personnel.")

Analysis: Stool samples are thawed on ice to remove a representative 1 gm sample for DNA extraction using the QiaAmp DNA Stool Mini Kit (Qiagen Sciences, Valencia, CA). The Kit's procedure is followed using the additional 5 min heating step at 95°C. The isolated DNA samples are subjected to *B. lactis* specific PCR analysis (See procedure in 8.1.5 PCR Verification of BB-12 Enumeration). A portion of the stool collected at each sampling point will be held at -70°C for possible future investigation.

In addition to stool analysis, we will ask parents to record how much yogurt their child consumed on a daily basis.

9 STUDY SCHEDULE

9.1 RECRUITMENT

Research staff will meet with area physicians via the CAPRICORN network and inform them about the study. All treating physicians at each office will alert patients who are being placed on an antibiotic for a respiratory infection that a research study examining the safety of a probiotic yogurt drink is being carried out by Georgetown University researchers. Flyers and posters will also be displayed in all offices participating in the study three months prior to initiation of the study.

If they meet basic entry criteria, the potential participant will be offered the opportunity for study participation and consent will be obtained. Information provided during the consent process include, the purpose of the study, procedures, withdrawal procedures, subject termination, risk/discomforts, benefits, costs, compensation, and alternative to participation.

9.2 ENROLLMENT/BASELINE

The enrollment/baseline visit will take place at the participants' homes or doctor's office where comfort and confidentiality is assured. The purpose of this visit is to have in-person time to collect baseline data, explain all forms, go over the schedule of visits and intervention, and give the participant the initial compensation.

The enrollment/baseline visit will be completed virtually, when public health guidelines recommend limiting in-person visits or when participants prefer a virtual visit.

Once it is confirmed that the parents/caregivers and child meets all inclusion and exclusion criteria, baseline data will be collected. These include: Baseline Health Status and Demographic Information.

Following the baseline procedures, the parents/caregivers will receive the BB-12 yogurt or control yogurt for days 1 through 7-10 to be given to their child once a day. In addition, they will also receive measuring cups that denote level of 4 ounces. The amount of BB-12 supplemented yogurt drink to be supplied will be 4 ounces per day, which is slightly more than 100 grams/day.

Parents/caregivers will be asked to collect a stool sample from their child prior to starting the yogurt. Stool for children who stool in a toilet will be collected via a stool hat and transferred to proper vials. Stools for children in diapers will be collected directly from the diapers. Stools will be collected multiple times throughout the study. Research staff will be trained on how to properly transport stool and how to instruct participants on collecting stool.

During the initial visit, parents/caregivers will also be given all materials to collect stools, the diary, and study materials as well as the initial compensation.

Following virtual enrollment/baseline visits, study supplies typically delivered at enrollment—prescribed investigational product (yogurt), forms for data collection, and kits for sample collection—will be delivered following the informed consent process and after all required signatures have been obtained.

9.3 TELEPHONE FOLLOW-UP

On the first day that the participant drinks the yogurt, parents will schedule a phone call for 30 minutes after the drink is consumed, to ensure any adverse events are recorded. Parents will alert study personnel what time their child will consume the first yogurt and study personnel will call the participant 30 minutes after to ensure that there are no side effects from the yogurt.

These follow-up phone visits will be completed on Days 7, 11, 14 and 180 (±2 days). It is imperative that all visits be completed on a timely and regular fashion.

Generally, the Follow-Up Form will be the only form completed during the phone calls, but at times depending on parent/caregiver's report, there may be another form or two.

The follow up period includes all the time previous to the day of the interview. Any incidents that happen the day of the visit would be captured in the next Follow Up Visit.

There will be a set day that each subsequent visit should be completed for each participant. The research personnel should call all parent/caregiver's phone numbers at least one time per day in order to collect the data. If more than 3 business days have passed from the set day, the RA should alert the PI that this week's Follow-Up Form has not yet been completed. If the RA is not able to contact the participant, a Missed Visit Report Form should be completed instead and the PI should be alerted once again.

If a participant is unmasked at any point in time in during the study, PI will be alerted immediately. A Georgetown University employee in the Department of Family Medicine not associated with the study will follow up with this participant from this point on. This particular research personnel is not to discuss any information regarding this occurrence with any other personnel other than the PI.

Additional stool samples will be collected on Days 7, 14, 21 and 30 (±2 days) (Table 8).

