5.2 Study Outcome Measures

5.2.1 Primary Outcome Measure

The primary outcome is clinically diagnosed diarrhea anytime within 14 days of enrollment. Diarrhea is clinically defined as three or more loose stools per day for two consecutive days. This will be a dichotomous (yes or no) outcome of diarrhea during the 14-day period.

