9.3.1 Telephone Follow Up Script

In general, the Day 7, 11, 14, and 180 (±2 days) follow up will be administered over the phone, but may be completed in person. These phone visits are when the primary data will be collected. It is imperative that all visits be completed on a timely and regular fashion.

- 1) *Drink Number:* Make sure the parent/caregiver has the correct drink number as you are completing the Follow-Up Form.
 - a) Ask the parent/caregiver the number on the drink bottles and this should be confirmed with the computer program provided by the data manager.
 - b) If this number is not consistent, the parent/caregiver should be alerted not to give their child any more drinks and the project coordinator should be immediately alerted after completing this week's Follow-Up Form
- 2) Daily Assessment Diary: Ask the parent/caregiver to collect the Daily Assessment Diary for the phone conversation. A lot of the information that will be collected on the Follow-Up Form has been collected by the parent/caregiver on their Daily Assessment Diary. If they have not been using the Daily Assessment Diary, please positively stress the importance of the Daily Assessment Diary.
- 3) Explain to parent/caregiver that we are supposed to fill out this Follow-Up Form today and it should take about 5 minutes.

4) Administer Follow-Up Form.

- When entering sick days, missing school or daycare, etc., this should be generally whole
 integers. However, it is possible that a child missed only 2 hours to go to the doctor. All
 numbers under 4 hours should be counted at 0.5 days, and all those above rounded up
 to next integer.
- The parent/caregiver needs to decide if any activities were missed due to an illness. This is for all illnesses, even those that we are not collecting data about.
- For some questions the RA may say, "Did your child visit a doctor?" A doctor is defined as any medical personnel in this study. Therefore, the parent/caregiver may say, "Never, but s/he saw a nurse practitioner." Please count this the same as seeing the doctor.
- Satisfaction Questions: Please provide the parent/caregiver with the numbers s/he stated the prior time for a comparison.
- Compliance: Please let the parent/caregiver know that we would like them to give their child the drink every day, but regardless, we appreciate their participation.
- Adverse Events: If the parent/caregiver believes any AE occurred, it is imperative that

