 the RA immediately fill out an AE Form, and if there are any SAE, alert the PI and project
 coordinator immediately.
- 5) Confirm the date and time for the next visit's call.

All interventions will be completed by week two of the trial. At day 180, participants will be queried for changes in baseline health, onset of new chronic medical conditions and non-routine medical visits in the past 6 months.

Table 8. Participant Timeline and Sample of Data Collection Schedule (N=300)

Study Day	0/1	2	7	10	11	14	21	30	180 ³
Enrollment (baseline health and demographics)	Х								
Antibiotics	→	→	→ or →	→					
Yogurt Interventions	→	→	→	→					
Fecal Sample Collection	Х		Х			Х	Х	Х	
Follow-up Data Collection			Χ		Χ	Х			Х
Daily Assessment Diary ¹	→	→	→	\rightarrow	\rightarrow	→			
16S rRNA Gene Sequences	Х		Х			Х	Х	Х	
Metatranscriptome Analysis ²	Х		Х						
PedsQL™	Х		Х			Х			
Diet Recall Diary (2 x 2 days)		→	→	→	→	→			
Clostridium difficile Analysis ²		→	→	→	→	→			
Adverse Event (AE) Reporting	→	→	→	\rightarrow	\rightarrow	\rightarrow	\rightarrow	\rightarrow	→

¹Participants keep a diary from Days 1 through 14 (collected on Days 7 and 15). Information on stool number, shape and consistency, health, use of interventions, symptomatic care, quality of life, and AEs. ²Will be conducted on all participants with clinically-defined diarrhea.

³Day 180 follow-up is required by the FDA for a safety measurement. On day 180 parents will be asked if they believe there were any additional AEs associated with the yogurt intervention that they have not reported during the previous data collection periods.

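### The last call that takes the primary data can close 1 to 3 days short of the 14-day endpoint window, and no passage makes the diary that covers those days decide the outcome

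*Combined protocol and SAP*

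**What the plan says.** All references are to the combined protocol and SAP.

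- **Endpoint (5.2.1).** The window is set first: "The primary outcome is clinically diagnosed diarrhea anytime within 14 days of enrollment". The case definition then needs a two-day run: "Diarrhea is clinically defined as three or more loose stools per day for two consecutive days". The result is a single yes or no per child.
- **Where the data are taken (9.3.1).** "These phone visits are when the primary data will be collected".
- **When, and what each call covers (9.3).** "These follow-up phone visits will be completed on Days 7, 11, 14 and 180 (±2 days"). On the span of each call, the section states: "The follow up period includes all the time previous to the day of the interview". Events on the call day itself are handled separately: "Any incidents that happen the day of the visit would be captured in the next Follow Up Visit".
- **The visit after Day 14 (9.3.1).** "At day 180, participants will be queried for changes in baseline health, onset of new chronic medical conditions and non-routine medical visits". Table 8, footnote 3, adds a question on further adverse events that parents link to the yogurt. No daily stool history is described.
- **The diary (Table 8, footnote 1).** It runs over Days 1–14 and is picked up on Days 7 and 15. It holds: "Information on stool number, shape and consistency, health, use of interventions, symptomatic care, quality of life, and AEs". Section 13.1 has it double-entered. Section 9.3.1 uses it as an aid to completing the Follow-Up Form and tells staff what to say when a family has not kept it.
- **Planned size and analysis (11.2, 11.3).** Rates of 0.22 v 0.08 with 150 per arm; power 0.92 at two-sided 0.05, and 90% at the final level of 0.029. The test is Fisher's exact, with the relative risk and its 95% interval as the measure of effect.

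**The concern.** The endpoint window and the phone recall do not end on the same day. Even a call made exactly on schedule stops at Day 13, and two earlier call days are equally compliant. The rule that passes call-day events forward works between Days 7, 11 and 14. After that it passes them to a call some five and a half months later that asks about other things.

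What is at stake is ascertainment of the only primary endpoint. A child whose first qualifying two-day run ends on or after the call day can be counted as a non-case. That child has a completed call, so it does not appear as lost to follow-up either. The diary and the Follow-Up Form can also disagree for the same child simply because they cover different days, and no rule says which prevails.

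**Working it through.** **1. The plan's own power.** Inputs from 11.2: p1 = 0.22, p2 = 0.08, n = 150 per arm. Pooled-variance normal approximation:

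power = Φ{ [ |p1 − p2| − z·√(2p̄(1−p̄)/n) ] / √(p1(1−p1)/n + p2(1−p2)/n) }, with p̄ = 0.15.

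The two standard errors are √(2 × 0.15 × 0.85/150) = 0.0412 and √((0.1716 + 0.0736)/150) = 0.0404.
- At 0.05 (z = 1.96): (0.14 − 0.0808)/0.0404 = 1.46, power 0.928 (stated 0.92).
- At 0.029 (z = 2.18): (0.14 − 0.0900)/0.0404 = 1.24, power 0.892 (stated 0.90).

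Both reproduce within rounding of the method. Exact Fisher power is 0.914 and 0.871.

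**2. Days covered by the last call.** A call on Day c covers Days 1 to c − 1. A case needs two consecutive days, and Days 1–14 contain 13 such pairs. A pair is lost to the phone when its second day is later than c − 1.

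| Call on Day | Recall ends | Endpoint days outside | Pairs outside |
|---|---|---|---|
| 12 | Day 11 | 3 | 3/13 (23%) |
| 13 | Day 12 | 2 | 2/13 (15%) |
| 14 | Day 13 | 1 | 1/13 (8%) |
| 15 | Day 14 | 0 | 0 |
| 16 | Day 15 | 0 | 0 |

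Three of the five permitted days, including the nominal one, fall short.

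**3. Size if the phone were the only source.** Assumptions: no diary recovery, first qualifying pairs spread evenly over the 13 positions (the documents give no onset distribution), and the same missed share f in both arms. Expected cases are 0.22 × 150 + 0.08 × 150 = 33 + 12 = 45. Observed rates are 0.22(1 − f) and 0.08(1 − f).

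| Calls | f | Cases missed | Difference | Relative risk | Pooled power at 0.029 | Fisher power at 0.029 |
|---|---|---|---|---|---|---|
| Full coverage | 0 | 0 | 0.140 | 0.364 | 0.892 | 0.871 |
| All on Day 14 | 1/13 | 3.5 | 0.129 | 0.364 | 0.859 | 0.832 |
| All on Day 12 | 3/13 | 10.4 | 0.108 | 0.364 | 0.772 | 0.732 |

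For calls spread evenly over Days 12–16, f = (3 + 2 + 1 + 0 + 0)/(5 × 13) = 9.2%. The difference is then 0.14 × 0.908 = 0.127. The factor (1 − f) cancels from the relative risk: 0.08/0.22 = 0.364 throughout.

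**4. With the diary counted.** The diary covers Days 1–14, so no endpoint day is uncovered for a child whose diary is returned and used. If diary availability is unrelated to outcome, the loss scales with the share of children without a usable late diary. Each 10 percentage points of such children costs about 0.1 × 3.5 = 0.35 case with Day 14 calls, or 0.1 × 10.4 = 1.0 case with Day 12 calls. The documents give no diary return rate.

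**5. Day numbering.** Table 8 labels enrollment Day 0/1, so 14 days from enrollment could end on Day 14 or Day 15. If it ends on Day 15, a Day 15 call and the Day 1–14 diary each stop one day short.

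**The case against.** The strongest answer is the diary. It records exactly what the case definition needs, runs to Day 14, is collected after the window closes, and is double-entered. Staff are told to encourage it, and Section 10.2 lists failure to complete it as a possible ground for withdrawal.

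There are other routes too. Section 13.1 lists a Diarrhea Report Form and a Diarrhea Follow-up Form. Diarrhea and loose stools are listed adverse events in Table 9, with reporting to Day 180. Section 10.1.2 keeps following expected events unresolved at the Day 14 follow-up. That last route matters most for a Day 14 call: the single lost pair, Days 13–14, begins inside the recall, so such a child might already be under follow-up. Section 9.3 describes only late slippage of calls, which causes no loss. The Follow-Up Form itself is not in the documents, so its stool item cannot be seen, and Section 9.3.1 speaks of primary data rather than the primary outcome.

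Most of this stands, and it rules out a stronger reading. A reader might infer that the call is the only source, that up to three endpoint days go unobserved, and that 4 to 10 cases will be recorded as non-cases. The documents do not support that: the days are observed wherever the diary is kept, returned and used, and the larger count needs every call on Day 12.

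What the objection does not supply is a rule. The only sentence that locates the primary data names the calls. No passage makes the diary decide the endpoint or requires it to be reconciled with the Follow-Up Form. Families without a diary are anticipated in 9.3.1, and the Appendix II substudy treats diary presence as a compliance measure. Adverse event follow-up helps only for symptoms already reported at the call, and no stated trigger ties the diarrhea forms to the uncovered days.

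**Conclusion.** The point holds as a gap in the ascertainment rules. A compliant final call on Days 12–14 leaves 1 to 3 endpoint days outside the phone recall, Day 180 as described does not recover them, and the source that does cover them is not given authority over the endpoint. A late case can therefore be missed when the diary is absent or not used.

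The risk differences of 0.129 (all calls on Day 14) and 0.108 (all on Day 12) are upper bounds as regards diary recovery. They also rest on even onset and equal loss by arm. Under the same assumptions the planned relative risk is not biased; the cost is some power and an understated risk difference. The actual loss depends on diary return and is probably small. This should be fixed because the remedy is cheap and stool days not recorded at the time cannot be reliably recovered later. It is not a must-fix defect.

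**What to change.** - In 9.3, the 9.3.1 script and Table 8, hold the final primary-outcome call no earlier than Day 15 (for example Days 15–17, in line with the Day 15 diary collection). Have it ask about each day through Day 14.
- Remove the deferral of call-day events to the following visit for this call.
- In 5.2.1 or 11.3, state that the Day 1–14 diary determines the endpoint, that the call fills days the diary lacks, and how a child is classified when the Day 15 diary is missing.
- Replace Day 0/1 with one numbering so that the end of the 14-day window is unambiguous. If the window is meant to end on Day 15, the diary and the earliest call day each move one day later.
- Check the reference in 10.1.2 to the Day 14 follow-up so that it agrees with the revised call.

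The cost is a few lines of text and a script edit, with no added contact. The downside is 1 to 3 more days of recall for families without a diary.
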